15. ADMINISTRATIVE AND LEGAL OBLIGATIONS

15.1 Protocol Amendments and Study Termination

All protocol amendments will be implemented by Syndax and must receive Health Authority (where required) and IRB/EC approval before implementation, except where necessary to eliminate an immediate hazard to patients. The Investigator **must** send a copy of the approval letter from the IRB/EC, along with the revised Informed Consent form, to Syndax or its representative.

Both Syndax and the Investigator reserve the right to terminate the study according to the study contract. The Investigator should notify the IRB/EC in writing of the study's completion or early termination and send a copy of the notification to Syndax or its representative.

15.2 Study Documentation and Archive

The Investigator must maintain a list of appropriately qualified persons to whom he/she has delegated study duties. All persons authorized to make entries and/or corrections on eCRFs will be included on the Syndax Delegation of Responsibility Form.

Source documents are original documents, data, and records from which the patient's eCRF data are obtained. These include but are not limited to hospital records, clinical and office charts, laboratory and pharmacy records, diaries, microfiches, radiographs, and correspondence.

The Investigator and study staff are responsible for maintaining a comprehensive and centralized filing system of study-related documentation, available for inspection and audit at any time by representatives from Syndax and/or applicable regulatory authorities. Elements should include:

- Patient files containing informed consent forms and patient identification list.
- Study files containing the Protocol with all amendments, Investigator's Brochure, copies of pre-study documentation ([Section 14.3](#)), and all correspondence to and from the IRB/EC and Syndax.
- Investigational Product Accountability Records and all drug-related correspondence.

In addition, all original source documents supporting entries on the eCRFs must be maintained and be readily available. Source documents should be retained by the investigator according to ICH-E6 and local regulations or as indicated in the clinical study agreement, whichever is longer.

No study document should be destroyed without prior written agreement between Syndax and the Investigator. Should the Investigator wish to assign the study records to another party or move them to another location, he/she must notify Syndax in writing of the new responsible person and/or the new location.

15.3 Study Monitoring and Data Collection

A study monitor will be responsible for contacting and visiting the Investigator for the purpose of inspecting the facilities; verifying the eCRFs at regular intervals throughout the study to assess adherence to the protocol; ensuring completeness, accuracy, and consistency of the data; and ensuring adherence to local regulations on the conduct of clinical research. The monitor should have access to patient medical records and other study-related records needed to verify the entries on the eCRFs.

The Investigator agrees to cooperate with the monitor to ensure that any problems detected in the course of these monitoring visits, including delays in completing eCRFs, are resolved.

In addition to routine monitoring and in accordance with United States 21 CFR Parts 312, 50, and 56, the ICH GCP and applicable local regulatory requirements, the study site may be selected for audit by a designee of Syndax or its representative and/or regulatory inspection by appropriate regulatory authorities. Inspection and audit of site facilities (i.e., pharmacy, drug storage areas, laboratories) and review of study-related records may occur to evaluate the study conduct and compliance with the protocol and applicable regulatory requirements.

Agreements between Syndax, the Institution and/or Principal Investigator regarding study payments, insurance coverages and publication policy are covered in the clinical trial agreement and not in this protocol.

17. APPENDICES

17.1 Appendix 1 New York Heart Association (NYHA) Classification of Heart Failure

Class	Symptomatology
I	No symptoms. Ordinary physical activity such as walking and climbing stairs does not cause fatigue or dyspnea.
II	Symptoms with ordinary physical activity. Walking or climbing stairs rapidly, walking uphill, walking or stair climbing after meals, in cold weather, in wind or when under emotional stress causes undue fatigue or dyspnea.
III	Symptoms with less than ordinary physical activity. Walking 1 to 2 blocks on the level and climbing more than 1 flight of stairs in normal conditions causes undue fatigue or dyspnea.
IV	Symptoms at rest. Inability to carry on any physical activity without fatigue or dyspnea.

17.2 Appendix 2 Concomitant Medications to be Avoided

Examples of sensitive *in vivo* CYP substrates and CYP substrates with narrow therapeutic range are summarized in [Table 17-1](#).

Table 17-1: Examples of substrates that may be affected by entinostat

CYP Enzymes	Substrates with narrow therapeutic range ¹
CYP1A2	Theophylline, tizanidine
CYP2C8	Paclitaxel
CYP3A ²	Alfentanil, astemizole ³ , cisapride, cyclosporine, dihydroergotamine, ergotamine, fentanyl, pimozide, quinidine, sirolimus, tacrolimus, terfenadine

¹ CYP substrates with narrow therapeutic range refers to drugs whose exposure-response relationship indicates that small increases in their exposure levels by the concomitant use of CYP inhibitors may lead to serious safety concerns (e.g. Torsades de Pointes).

2 Because a number of CYP3A substrates (e.g. darunavir, maraviroc) are also substrates of P-gp, the observed increase in exposure could be due to inhibition of both CYP3A and P-gp.

3 Withdrawn from the United States market because of safety reasons.

Table 17-2 P-gp Inhibitors and Inducers

	Inhibitor	Inducer
P-gp, MDR1	Amiodarone, azithromycin, captopril, carvedilol, clarithromycin, conivaptan, diltiazem, dronedarone, felodipine, lopinavir, quercetin, ranolazine, ticagrelor, ritonavir, cyclosporine, verapamil, erythromycin, ketoconazole, itraconazole, quinidine	Avasimibe, carbamazepine, phenytoin, rifampin, St John's Wort, tipranavir/ritonavir

17.3 Appendix 3: Pre-existing Autoimmune Diseases

Subjects should be carefully questioned regarding their history of acquired or congenital immune deficiencies or autoimmune disease. Subjects with any history of immune deficiencies or autoimmune disease listed in the table below are excluded from participating in the study. Possible exceptions to this exclusion could be subjects with a medical history of such entities as atopic disease or childhood arthralgias where the clinical suspicion of autoimmune disease is low. Patients with a history of autoimmune-related hypothyroidism on a stable dose of thyroid replacement hormone may be eligible for this study. In addition, transient autoimmune manifestations of an acute infectious disease that resolved upon treatment of the infectious agent are not excluded (e.g., acute Lyme arthritis). Contact the Medical Monitor regarding any uncertainty over autoimmune exclusions.

Acute disseminated encephalomyelitis	Dermatomyositis	Neuromyotonia
Addison's disease	Dysautonomia	Opsoclonus myoclonus syndrome
Ankylosing spondylitis	Epidermolysis bullosa acquista	Optic neuritis
Antiphospholipid antibody syndrome	Gestational pemphigoid	Ord's thyroiditis
Aplastic anemia	Giant cell arteritis	Pemphigus
Autoimmune hemolytic anemia	Goodpasture's syndrome	Pernicious anemia
Autoimmune hepatitis	Graves' disease	Polyarteritis nodosa
Autoimmune hypoparathyroidism	Guillain-Barré syndrome	Polyarthritis
Autoimmune hypophysitis	Hashimoto's disease	Polyglandular autoimmune syndrome
Autoimmune myocarditis	IgA nephropathy	Primary biliary cirrhosis
Autoimmune oophoritis	Inflammatory bowel disease	Psoriasis
Autoimmune orchitis	Interstitial cystitis	Reiter's syndrome
Autoimmune thrombocytopenic purpura	Kawasaki's disease	Rheumatoid arthritis
Behcet's disease	Lambert-Eaton myasthenia syndrome	Sarcoidosis
Bullous pemphigoid	Lupus erythematosus	Scleroderma
Chronic inflammatory demyelinating polyneuropathy	Lyme disease - chronic	Sjögren's syndrome
Chung-Strauss syndrome	Meniere's syndrome	Stiff-Person syndrome
Crohn's disease	Mooren's ulcer	Takayasu's arteritis
	Morphea	Ulcerative colitis
	Multiple sclerosis	Vogt-Kovanagi-Harada disease
	Myasthenia gravis	Wegener's granulomatosis

17.4 Appendix 4: Immune-related Response Criteria Derived from RECIST 1.1 (irRECIST)

Increasing clinical experience indicates that traditional response criteria may not be sufficient to fully characterize activity in this new era of targeted therapies and/or biologics. This is particularly true for immunotherapeutic agents such as anti-CTLA-4 and anti-PD1\anti PDL1 which exert the antitumor activity by augmenting activation and proliferation of T cells, thus leading to tumor infiltration by T cells and tumor regression rather than direct cytotoxic effects (Hoos 2010; Hodi 2008). Clinical observations of patients with advanced melanoma treated with ipilimumab, for example, suggested that conventional response assessment criteria such as RECIST and WHO criteria are not sufficient to fully characterize patterns of tumor response to immunotherapy because tumors treated with immunotherapeutic agents may show additional response patterns that are not described in these conventional criteria (Hoos 2010; Nishino 2014).

Furthermore, the conventional tumor assessment criteria (RECIST and WHO criteria) have been reported as not capturing the existence of a subset of patients who have an OS similar to those who have experienced CR or PR but were flagged as PD by WHO criteria (Hoos 2010; Nishino 2012).

On these grounds, a tumor assessment system has been developed that incorporates these delayed or flare-type responses into the RECIST 1.1 criteria (irRECIST; Nishino 2014).

Lesion measurability and baseline selection of lesions:

The RECIST 1.1 definitions for measurable and non-measurable lesions apply. At baseline, all tumor lesions/lymph nodes will be categorized as measurable or non-measurable. For target lesions, a Total Measured Tumor Burden (TMTB) for all target lesions will be calculated and reported as the baseline TMTB (similarly to the Sum of Diameters in RECIST 1.1). The baseline TMTB will be used as reference to further characterize any objective tumor response in the measurable dimension of the disease.

New lesions:

irRECIST do not necessarily score the appearance of new lesions as progressive disease. Also, new lesions should be categorized as measurable or non-measurable (same measurability rules as RECIST 1.1. apply).

In order to be selected as new measurable lesions (≤ 2 lesions per organ, ≤ 5 lesions total, per timepoint), new lesions must meet criteria as defined for baseline target lesion selection and meet the same minimum size requirements of 10 mm in long diameter and minimum 15 mm in short axis for new measurable lymph nodes. New measurable lesions shall be prioritized according to size, and the largest lesions shall be selected as new measured lesions.

All new lesions not selected as New Measurable lesions are considered New Non-measurable lesions and are followed qualitatively.

Post baseline tumor assessments:

- TMTB: At each post-baseline assessment the TMTB is defined as the sum of:
 - o Longest diameters of all non-nodal target lesions
 - o Longest diameters of all NEW non-nodal measurable lesions
 - o Short axis of all nodal target lesions
 - o Short axis of all NEW nodal measurable lesions
- Non-target lesions/New Non-measurable lesions: the RECIST 1.1 definitions for the assessment of non-target lesions apply (irCR; irNN, irPD).

Overall response at each time point:

- Immune-related complete response (irCR): Complete disappearance of all lesions (whether measurable or not) and no new lesions. All measurable lymph nodes also must have a reduction in short axis to <10 mm.
- Immune-related partial response (irPR): Decrease of $\geq 30\%$ in TMTB relative to baseline, non-target lesions are irNN, and no unequivocal progression of new non-measurable lesions
- Immune-related stable disease (irSD): Failure to meet criteria for irCR or irPR in the absence of irPD.
- Immune-related progressive disease (irPD): Minimum 20% increase and minimum 5 mm absolute increase in TMTB compared to nadir, or irPD for non-target or new non-measurable lesions.
- irNE (Not evaluable): used in exceptional cases where insufficient data exists.

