10.3.1 Tumor Measurements and Disease Response Assessment

10.3.1.1 Tumor Measurement and Assessment

Initial tumor imaging at screening must be performed within 28 days prior to initial study drug dosing (C1D1). (Scans performed as part of routine clinical management are acceptable for use as initial tumor imaging if they are of diagnostic quality and performed within 28 days prior to C1D1 and can be assessed by the central imaging vendor.) Patients will have radiological disease assessments performed every 6 weeks (+/-3 days) (Week 6, Week 12, etc.) during study treatment through week 36 or until progressive disease. If progressive disease has not

occurred by week 36, radiological assessments will be then be done every 9 weeks (+/-3 days) until progressive disease. If a patient comes off study for reasons other than progressive disease, radiological assessments will continue on this same study schedule until progressive disease is unequivocally documented. Images should be kept to the calendar schedule and not be delayed for delays in cycles or study drug administration. Disease response in target and non-target lesions will be assessed locally by the Investigator using RECIST 1.1 and irRECIST.

Measurable Disease

To be eligible for study participation, all patients must have documented measurable disease per RECIST 1.1 that has been radiologically documented within 28 days prior to initiating study drug treatment, defined as follows:

At least 1 measurable lesion:

- ≥ 10 mm in longest diameter on an axial image by CT scan or MRI with ≤ 5 mm reconstruction interval
 - If slice thickness is greater than 5 mm, longest diameter must be at least 2 times the thickness
- ≥ 20 mm longest diameter by chest X-ray (if clearly defined and surrounded by aerated lung); CT is preferred, even without contrast.
- Lymph nodes ≥ 15 mm in short axis on CT scan (CT slice thickness of ≤ 5 mm)

If there is only 1 measurable lesion and it is located in previously irradiated field, it must have demonstrated progression according to RECIST 1.1.

Non-measurable Lesions

Non-measurable lesions are defined per RECIST 1.1 as the following and should be captured and followed accordingly and within the eCRF according the eCRF guidelines.

- Masses < 10 mm
- Lymph nodes ≥ 10 to < 15 mm in short axis
- Leptomeningeal disease
- Ascites, pleural or pericardial effusion
- Inflammatory breast disease (cont'd on next page)
- Lymphangitic involvement of skin or lung

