4.2.2 Secondary Efficacy Endpoints

- PFS determined by the local investigator using irRECIST
- ORR (CR or PR) by RECIST 1.1
- ORR (irCR or irPR) by irRECIST
- CBR (CR, PR or SD for at least 24 weeks) by RECIST 1.1
- CBR (irCR, irPR, or irSD for at least 24 weeks) by irRECIST
- OS

In patients who experience a response to treatment based on RECIST 1.1 (CR or PR) or on irRECIST (irCR or irPR):

- DOR
- TTR

**Statistical Analysis Plan
SNDX-275-0602 (TRIO025)
DM-025-037**

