6.2 Objective Response Rate (ORR)

ORR is defined as the crude proportion of patients achieving a best overall response of CR or PR assessed using RECIST 1.1. The best overall response assessed using irRECIST will also be analyzed separately and the corresponding ORR will be calculated. The overall response will be determined locally by the investigator at each scheduled assessment.

Per protocol (Section 10.3.1.3), partial or complete response should be confirmed by a repeat tumor imaging assessment not less than 4 weeks from the date the response was first documented.

The following table will be followed to assign a best overall response based on the achievement and confirmation of two consecutive assessments according to RECIST 1.1:

Overall response First time point	Overall response Subsequent time point (at Least 4 Weeks Later)	Best Overall Response
CR	CR	CR

**Statistical Analysis Plan
SNDX-275-0602 (TRIO025)
DM-025-037**

Overall response First time point	Overall response Subsequent time point (at Least 4 Weeks Later)	Best Overall Response
CR	PR	PR
CR	SD	SD
CR	PD	PD
CR	NE	SD
PR	CR	PR
PR	PR	PR
PR	SD	SD
PR	PD	PD
PR	NE	SD

$$ORR_{RECIST1.1} = \frac{\# \text{ of patients with best overall response as CR or PR}}{\text{Total number of patients}}$$

Similarly, irCR or irPR based on irRECIST will also be confirmed.

The following table is therefore used for best overall response based on irRECIST:

Overall response First time point	Overall response Subsequent time point (at Least 4 Weeks Later)	Best Overall Response
irCR	irCR	irCR
irCR	irPR	irPR
irCR	irSD	irSD
irCR	irPD	irPD
irCR	irNE	irSD
irPR	irCR	irPR
irPR	irPR	irPR
irPR	irSD	irSD
irPR	irPD	irPD
irPR	irNE	irSD

And ORR based on irRECIST is calculated as follows:

$$ORR_{irRECIST} = \frac{\# \text{ of patients with best overall response as irCR or irPR}}{\text{Total number of patients}}$$

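### Appendix 4 makes irNN a condition of irPR, so a patient with TMTB down at least 30%, measured disease remaining and non-target disease cleared is scored irSD

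*Protocol*

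**What the plan says.** Protocol Section 17.4 (Appendix 4) holds the irRECIST rules.

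- **Non-target states.** "the RECIST 1.1 definitions for the assessment of non-target lesions apply (irCR; irNN, irPD" gives three states. The appendix does not spell out irNN, but its place beside irCR and irPD makes it the state in which disease has neither cleared nor progressed.
- **irPR.** A fall of at least 30% "in TMTB relative to baseline, non-target lesions are irNN, and no unequivocal progression of new non-measurable lesions".
- **irCR.** "Complete disappearance of all lesions (whether measurable or not) and no new lesions", with measurable nodes also below 10 mm in short axis.
- **irSD.** Whatever is left: "Failure to meet criteria for irCR or irPR in the absence of irPD".
- **TMTB.** After baseline it sums target lesions and new measurable lesions.

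For entry, Protocol Section 10.3.1.1 asks for "At least 1 measurable lesion". It does not ask for non-target disease.

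SAP Section 4.2.2 lists "ORR (irCR or irPR) by irRECIST" as a secondary endpoint. In SAP Section 6.2, "The overall response will be determined locally by the investigator at each scheduled assessment". The formula introduced by "And ORR based on irRECIST is calculated as follows" counts only best responses of irCR or irPR. Its confirmation table maps irPR followed by irSD to irSD. The SAP has no irRECIST time-point rule of its own, and nothing else in either document widens the irPR condition.

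**The concern.** The irPR rule names one non-target state where two should qualify. Of two patients with the same fall in TMTB, the one whose non-target disease has gone receives the lower category. That ordering cannot be intended.

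Four secondary endpoints depend on the category: irRECIST ORR, CBR, DOR and TTR. Investigators assign it locally, and Protocol Section 6.2 plans up to about 50 centers. Some may apply the text literally and others may score irPR by common sense, so the endpoints would depend partly on how each site reads one line.

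**Working it through.** There is no stated figure to reproduce. The check is to run the Appendix 4 definitions through every relevant combination.

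**Step 1. Time-point category.** Assume TMTB is down at least 30% from baseline, with no increase that meets irPD and no new non-measurable lesions.

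| Non-target status | Measured disease | As written | With the fix |
|---|---|---|---|
| irNN | remains | irPR | irPR |
| irCR | remains | **irSD** | irPR |
| none at baseline | remains | **undefined** | irPR |
| irNN | all gone | irPR | irPR |
| irCR or none | all gone | irCR | irCR |
| irPD | any | irPD | irPD |

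In the second row irCR fails because measured disease remains, irPR fails because non-target status is not irNN, and irPD is absent. Only irSD is left. The remaining disease may be a new measurable lesion: if all baseline disease clears but such a lesion keeps TMTB above zero, the result is the same.

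In the third row a reader who requires the status to equal irNN reaches irSD. A reader who treats a condition on absent lesions as met reaches irPR. The text does not choose.

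**Step 2. Best overall response under SAP Section 6.2.** Take a patient whose measured disease persists and whose non-target lesions clear at some scan.

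- Clearance at the first scan with a 30% fall: irSD there and while that state lasts, so no irPR.
- Clearance between the first irPR scan and its confirmation: irPR then irSD, which maps to irSD. The response is lost.
- Clearance after irPR on two consecutive scans: irPR is already confirmed and is kept.

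**Step 3. Endpoints reached.**

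- irRECIST ORR: the patient leaves the numerator.
- irRECIST DOR and TTR (SAP Sections 6.5 and 6.6): she leaves the responder set.
- irRECIST CBR (SAP Section 6.3): irPR counts whatever its length; irSD counts only if it lasts at least 24 weeks.
- irRECIST PFS: irPD is defined without reference to irPR or irNN, so it does not change.
- Primary PFS: uses RECIST 1.1, so it does not change.

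**Step 4. Direction.** The fix moves patients only from irSD or undefined to irPR, and none the other way. Literal application can therefore only lower irRECIST ORR.

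**Step 5. Size.** Protocol Section 6.3 plans 35 patients per arm, so one misclassified patient is 1/35 = 2.9 percentage points. Beyond that, let p be the ORR under the fixed rule and q the share of those responders lost under the literal rule. Then scored ORR = p × (1 − q). The documents do not give q, and p is uncertain too: the only response rate given, 18–19% in Protocol Section 5.2, is for PD-L1-positive patients, and eligibility does not select on PD-L1. The p values of 10% and 30% and all q values below are assumptions.

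| p | q = 10% | q = 25% | q = 50% |
|---|---|---|---|
| 10% | 9.00% | 7.50% | 5.00% |
| 18.5% | 16.65% | 13.88% | 9.25% |
| 30% | 27.00% | 22.50% | 15.00% |

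This shows sensitivity only. It is not an estimate.

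**The case against.** The best case against is that this is a drafting slip with a narrow reach. A sensible investigator will score the affected patient irPR. Responders confirmed before clearance are kept, and those whose measured disease also disappears, with no new lesions, become irCR. RECIST 1.1 ORR and CBR are reported separately.

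Discrepancies could also be seen. SAP Section 11.2 lists lesion measurements beside the time-point response under both criteria, and Section 11.3 plans waterfall and spider plots for both. SAP Section 9.1 has outputs reviewed in dry runs. Protocol Section 10.3.1.3 sends scans of investigator-assessed responders to the core laboratory.

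The limits on reach stand. The safeguards make a misclassification visible but give nobody a rule for correcting it. The core laboratory step is triggered by a response call, so a patient scored irSD reaches it only through a RECIST 1.1 response or at the Sponsor's direction. Reliance on common sense concedes that the written rule will not be followed uniformly.

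A reader might go further in three ways, none of which the documents support:

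- **That every patient without non-target lesions is scored irSD.** The text leaves her status open.
- **That irRECIST ORR will be understated by a particular amount.** This needs a share of affected responders that the documents do not contain, and a response rate for this population rather than a PD-L1-positive one.
- **That the treatment comparison is biased.** Both blinded arms use the same rule, and nothing shows that it removes more responders from one arm.

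**Conclusion.** The point holds in a limited form. As written, Appendix 4 gives a wrong result in one cell: TMTB down at least 30%, target or new measurable disease remaining, non-target irCR. It gives no result in another: no non-target lesions at baseline. The first conclusion rests only on the appendix wording, which lists irCR and irNN as distinct states.

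The loss falls on patients whose non-target disease clears before irPR is confirmed, at sites that apply the text literally. It touches irRECIST ORR, DOR, TTR and, for shorter irSD, CBR. Its direction for ORR is known (downward); its size is not. This is a wording error in secondary endpoints that should be corrected. It does not threaten the primary analysis.

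**What to change.** In Appendix 4, keep the 30% TMTB threshold and the condition on new non-measurable lesions. Change the middle condition of irPR so that it is met when non-target lesions are irCR or irNN, or when none were present at baseline. Do not extend it to non-target lesions that were not evaluated: the appendix gives no support for that, and it reserves irNE for insufficient data.

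Also add a programmed check that compares each irRECIST time-point category with the TMTB change and the non-target status and queries mismatches.

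No new data or patient procedures are needed. The wording is protocol text, however, so under Protocol Section 15.1 the change needs an amendment with IRB/EC approval and, where required, Health Authority approval. The edit check must also be programmed.
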